## I. INTRODUCTION TO RESUBMISSION APPLICATION (1 R01 DA040966-01A1)

We thank the reviewers for their valuable comments on the previous application. We combined the concerns in resume/summary ("S") and critiques ("C") and grouped them in sections. Changes in the proposal are bracketed.

**Significance:** 1. *Practical utility of fMRI* (C2). We agree that fMRI is currently fiscally impractical, but believe that will change rapidly. In the interim, fMRI has significant contributions to make, as the reviewer acknowledges: "mechanistic knowledge may guide interventions... by identifying critical circuits and associated psychological functions..." This study will offer insights on how to merge neuroscience methods and prevention science as this tool becomes more integrated in the direct assessment of programmatic effects, and offer guidance on how to personalize prevention program exposure, addressing continuing concerns about specificity and dosage (**III B**).

**Investigators:** 1. *Delay in start-up* (C3). We do not anticipate undue delay in the start-up of this project because of personnel issues. [name] center has staff members on board who are experienced in coordinating various types of studies and research activities related to behavioral and mental health. The center has had continuous NIH funding since its inception 28 years ago. The research staff transition from one study to the next based on the funding cycles of the research projects in the center. In addition, the center has decades of experience in successfully recruiting and training personnel for research projects. We have access to a large pool of qualified candidates to attract to these positions, given that we have five local universities along with two medical centers.

2. *Collaboration history* (S, C3). In addition to acquiring pilot data, the team has worked collaboratively on other projects and grant proposals (**IIIC.2; [name] Biosketch**). As cited in the resume/summary (S), [name] has an established record of successfully completing collaborative, multi-disciplinary studies and publishing their results.

**Innovation:** We very much appreciate all the positive comments. No weaknesses were identified in this section.

**Approach:** 1. *Analysis of multiple measures* (S, C1). PAAS is a family intervention. Data from PAAS and SAAF indicated that the intervention has both direct and indirect effects. Positive parenting improves self-regulation in offspring around pubertal transition which, in turn, protects these youth against behaviors associated with HIV/ AIDS and substance abuse risk as they progress through middle and late adolescence (**IIIC.3b, Figure 2**). Here, we will examine the effects of parenting on youth's neurobiological changes in exploratory analyses (**II, IIIC.7d.3**).

2. *How fMRI tasks reflect PAAS' effects on regulation processes* (S, C1). The primary fMRI task is a decision-making task in the context of risk/reward opportunities, and this task targets both socio-emotional and cognitive-control neural substrates (**IIIC.3c, Fig 3**). Behavioral performance on this task is related to reward-seeking traits and risky behaviors in real life. PAAS targets developmental vulnerabilities and exploits sensitivity to rewards by incentivizing cognitive-control functioning by enhancing youth's resistance efficacy skills and raising awareness of the association between risk engagement and compromised future goals (**IIIC.3b, Fig 2; IIIC.4f.6, Table 2**). To ensure risky decision-making is not confounded by poor impulse control, we included a control task (**IIIC.1**).

3. *Handling confounds* (S, C1). Youth on medications affecting the brain, with behavioral/emotional problems at a clinical level, or those using alcohol/drugs three days prior to the fMRI scans will be excluded (**IIIC.4c**). We proposed standardized assessments and urine drug screens to evaluate these factors (**IIIC.4f.3, Table 1**).

4. *Wait-list control* (C2). The intervention's efficacy was proven in randomized, controlled trials and psychological "active ingredients" were identified. The focus of this proposal is on their underlying neurobiological substrates. The wait-list control does not account for "general" (attention) effects. PAAS-tech does not involve a therapist, so this is not an issue. This control provides greater statistical power to detect group differences in addition to the benefit of a proven intervention for the control group after completing the experimental phase (**Fig6; IIIC.10c**).

5. *Quality control imaging data* (C2). The pilot data were in 9-12 or 12-18 year-olds, which cover the age range (i.e. 11-13 years) in the proposed study (**IIIC.3**). Our neuroimaging studies have included youth as young as 6 years, with reliable data in 93%-97% of the samples (**IIIC.4f.2b.2**). We implement many reliable data collection methods (**IIIC.4f.2b.1, 2b.2**). We also institute established methods to reduce dropout rates (**IIIC.10a**). So, the estimated 20% dropout rate is easily attainable. Should this not prove to be the case, we agree with the reviewer: "this concern is mitigated by the robust recruitment mechanisms in place which could supply additional subjects."

6. *Motion artifacts* (C2). We propose several methods to address motion artifact at individual level. These metrics can be summarized to a single number and then compared between groups or used as covariates (**IIIC.4f.2b.6**).

7. *Power analysis* (C2). To avoid biased estimates from small sample sizes, we used *minimum detectable effect size* (ES) at a clinically meaningful level. ES from pilot data (.3-.5) are consistent with the power analysis (**IIIC.7e**).

8. *fMRI tasks not novel* (C3). We deliberately selected theoretically-based, well-established tasks in this novel study on neural basis of a prevention program. Untested tasks could lead to confounds in interpreting the results.

9. *Miscellaneous*. IQ should be  $\geq 80$  (C3). We will provide laptops to those who don't own them (C3; **IIIC.4f.6**).

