### III C. APPROACH

**IIIC.1 Overview:** The conceptual model guiding our study is presented in **Fig 1**. Aim 1 will assess the effects of PAAS on the magnitude of Phase 2 functional connectivity between reward-drive and cognitive-control neural circuitry at rest and during a decision-making task after controlling for pre-intervention (Phase 1) levels. Aim 2 will evaluate if Phase 2 post-treatment neural circuitry changes mediate PAAS' effects on psychological processes (i.e. cognitive and emotional self-regulation) at the 3-month follow-up (Phase 3) after controlling for Phase 1 values. Our overarching hypothesis is that the functional connectivity between reward and cognitive-control networks correlates with self-regulation, and that PAAS increases the magnitude of functional connectivity between these neural networks. In addition to these hypotheses, we will identify characteristics (demographic, neurobiological, psychological, behavioral and social-contextual factors) that moderate PAAS' effects on the relationship between functional brain changes and cognitive-emotional self-regulation in exploratory analyses (IIIC.3b; **Fig 2**).

A total of 128 AA volunteers (ages 11-13 years, 50% male and female) and 128 parents (primary caretakers) will be recruited. Youth and parents will complete assessments on intervention targets (i.e. parenting processes, youth psychological protective factors and cognitions/behaviors associated with HIV and SUD vulnerability). fMRI scans will be acquired in the youth to assess functional connectivity between reward-drive and cognitive-control neural circuitry during rest and while performing a decision-making task involving probabilistic monetary rewards. A second task that assesses general impulsivity/motor response inhibition (in contrast to reward-drive) will be included as a supplementary measure. Following assessments, the families will be randomized to either PAAS or a wait-list control condition for 6 weeks. fMRI scans will be repeated after 6 weeks to measure functional brain changes from pre-to-post intervention. They will repeat the intervention-targeted assessments 3 months later, after which the wait-list controls will be offered PAAS as a benefit for participation in the study (IIIC.4f.1; **Fig 6**).

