**IIIC.4f.2b.3. The WOF Task:** This task allows for the analysis of both risk-seeking and risk-avoidance (Fig 7). During each trial, the participants will be shown a wheel on which the probabilities of winning and losing points are shown as pink and yellow sections, respectively. The number of points that can be won or lost is printed on the wheel sections. The words “Bet” and “Pass” are displayed each time, prompting participants to select one or the other. For the present study, this “decision phase” is the period of interest. After 3 seconds, the wheel spins for a variable, randomly jittered period (1, 3, 5, or 7 sec), and the final result is displayed for 1 sec. If participants choose to bet, and the wheel lands on the pink section, they win the points indicated. Conversely, if the wheel lands on the yellow section they lose the number of points shown. These amounts will be added (or subtracted) to a running total that is not revealed until the end of the task. If participants choose to pass, they still see the outcome but no points will be added or deducted.

Win amounts are kept constant while probability and loss amounts are manipulated orthogonally resulting in 6 different wheels that represent 4 win/loss ratios (100/0, 60/40, 40/60, 0/100) and 2 levels of expected value (EV; +12 and -12). Participants are not explicitly told about the uniformity of expected values. The 0/100 wheel (100% chance of losing 12 points) and the 100/0 wheel (100% chance of winning 12 points) serve as no-risk control conditions and each is presented 8 times. Each 40/60 and 60/40 wheel (EV+ and EV-) is presented 22 times across 4 blocks. Behavioral outcomes include risk-seeking (percent of trials betted), risk-avoidance (percent of trials passed), and response times across conditions of varying probabilities and expected values. We found no practice effects with repeated tasks in at-risk adolescents during longitudinal follow-up ([name], unpublished data).

**IIIC.4f.2b.4. Go/No-Go Task:** The task assesses behavioral responses, with the subjects selectively responding to target stimuli (“X” ~.80 probability) and inhibiting responses to infrequent non-target stimuli (“K”~.20 probability; **IIIC.3d**). The task consists of two runs, with 245 trials per run (7 min) and a random inter-stimulus interval.

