**IIIC.4f.2b.5 Quality Assurance (QA):** Weekly QA data will be collected using the American College of Radiology Phantom Test Guidance Manual. The Functional Biomedical Informatics Research Network QA protocol will be used so that changes in image characteristics over the study period can be monitored and corrected.

**IIIC.4f.2b.6. fMRI Data Processing and Analysis:** Each participant's functional images (rest and task) will be corrected for head motion and co-registered to a common atlas space, then smoothed with a 6 mm kernel. After initial pre-processing, the time series at each voxel will have white matter, cerebrospinal fluid and motion-related signals removed via regression, and will be low-pass filtered at 0.1 Hz to retain low frequencies relevant for connectivity estimation. Head motion can still be a significant confound in fMRI connectivity studies, particularly in children. Hence, we will identify volumes that show large displacement (>0.5mm) or large change in global signal (>0.5%) relative to the preceding volume, and remove them prior to connectivity analysis. [The resulting 3 metrics can be summarized to a single number and then compared between groups or used as covariates.]

For the task-based data, event-related neural responses will be modeled with separate canonical hemodynamic response functions for each of the conditions (e.g. wheel types). For instance, BOLD responses to Risk vs. No-Risk trials will be compared, within/across probabilities and expected values. Group-level analysis will compare the trials during which the participants passed the trials (risk-avoidance) to trials where they bet. For the Go/No-Go task, successful Go trials will be compared to both successful and unsuccessful No-Go (inhibition) trials.

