5	Protecting against dangerous behavior	Understand risk prevalence, overall and for your community; Importance of being an approachable parent	Peer pressure; parents' concerns about peer affiliation	Identify peer pressure; compare risk engagers from non-risk engagers; dealing with temptation; prosocial peer affiliation	Caregivers and youth working together to protect youth from risk behaviors	Develop family plan for handling peer pressure and temptation; share expectations and values about risk and friendship
6	Parental protections that reduce high risk behaviors	Learn how to effectively monitor youth; understand the prevalence of sexual activity in teens; establish expectations about sex	Dealing with sexual and substance use temptations	Identifying and avoiding dangerous situations; connecting temptations, dreams, goals, school and future orientation	Our family plan and pledge for positive youth development	Share expectations, dreams, and hopes; discuss/identify family strengths; establish a family creed of strength, growth and competence

**IIIC.5. Primary Outcome Criteria:** Primary outcome variables include fronto-striatal functional connectivity at rest and while performing the WOF task and youth psychological protective factors (cognitive and emotional self-regulation). Other neural measures/circuits, psychological/social-contextual and behavioral variables (**Appendix 1**) will be used either as supplementary measures or as potential covariates. By sharpening our focus to *a priori* specified neural circuits and psychological measures, we hope to increase statistical power and, in turn, our ability to identify important differences in the responses of these circuits according to youth protective factors.

**IIIC.6. Sample Attrition:** The team has experience with intensive longitudinal studies involving difficult-to-reach samples with retention rates exceeding 90% for short-term follow-up (**IIIC.10a**). Even with a liberal estimate of 20% attrition, we will have 102 participants, which will give us sufficient power to detect medium effects (**IIIC.7e**).

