### IIIC.7. Statistical Methods

**IIIC.7a. Data Management:** Data management will be done via remote electronic data capture (*REDCap*). REDCAP was developed at VUMC to insure data integrity and completeness, including compliance with HIPAA (over 300,000 users). Data will be entered immediately after testing on data entry screens designed to duplicate the data collection forms (ACASI; **IIIC.4f.4**). Reports can be generated to track all contacts with the participants.

**IIIC.7b. Procedures for Handling Missing Data:** Missing data will be accounted for by including "missingness" as a covariate if the proportion of missing data is small, or alternatively using multiple imputation methods if the proportion of missing data is large, e.g. >5%.

**IIIC.7c. Data Reduction:** Each hypothesis will be examined using a primary variable, with supplemental information gained from analysis of other related measures (**see IIIC.5**).

**IIIC.7d. Data Analysis:** Descriptive statistics (e.g. means and standard deviations, frequencies and histograms) will be computed for all variables, along with 95% bootstrap confidence intervals. Significance tests will be two-tailed, with  $p < 0.05$ , controlling for multiple comparisons. Pubertal stage/gonadal hormones, gender and SES will be included as concomitant variables in analyses where they are known to correlate with the outcome. These covariates, while not of primary interest, will reduce residual variance and increase the precision of effect estimates for improved statistical power. Secondary analyses will determine if these covariates significantly affect the outcomes. Behavioral/emotional problem score (CBCL/YSR), lifetime history of substance use and dose of the intervention (number of completed sessions) will serve as additional potential covariates.

**IIIC.7d.1. Hypothesis 1:** PAAS will induce greater functional connectivity changes in the reward-drive and cognitive-control (fronto-striatal) circuitry compared to the wait-list condition. Post-treatment neural connectivity

scores will be regressed on group assignment (PAAS vs. wait-list) as the independent variable and baseline (pre-treatment) neural connectivity score as a covariate. Two separate models will be run for resting-state and task-based fMRI connectivity measures. Other covariates (IIIC.7d) will be included if there are group differences.

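### Go/No-Go is included to rule out confounding by poor impulse control, but no H1 or H2 model uses it, which leaves H2 path b open to that confounder

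*Combined protocol and SAP*

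**What the plan says.** In section I (Approach, item 2) the plan answers a question about how the fMRI tasks reflect PAAS effects: "To ensure risky decision-making is not confounded by poor impulse control, we included a control task". It refers the reader to IIIC.1, which says: "A second task that assesses general impulsivity/motor response inhibition (in contrast to reward-drive) will be included as a supplementary measure".

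The task is specified in IIIC.4f.2b.4: "The task consists of two runs, with 245 trials per run (7 min) and a random inter-stimulus interval". Its one named contrast is in IIIC.4f.2b.6: "For the Go/No-Go task, successful Go trials will be compared to both successful and unsuccessful No-Go (inhibition) trials".

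IIIC.5 defines the main endpoints: "Primary outcome variables include fronto-striatal functional connectivity at rest and while performing the WOF task", together with the youth protective factors. Other neural, psychological and behavioural variables "will be used either as supplementary measures or as potential covariates". IIIC.7c adds: "Each hypothesis will be examined using a primary variable, with supplemental information gained from analysis of other related measures".

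For H1 (IIIC.7d.1), post-treatment connectivity is regressed on group and baseline connectivity: "Two separate models will be run for resting-state and task-based fMRI connectivity measures". The IIIC.7d covariates enter only if the groups differ on them. Those covariates are pubertal stage or hormones, gender, SES, the CBCL/YSR problem score, lifetime substance use and number of completed sessions.

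For H2 (IIIC.7d.2), path b regresses 3-month self-regulation on the neural mediator and adjusts for the intervention. IIIC.1 says that Aim 2 also controls for Phase 1 values, but IIIC.7d.2 does not repeat this.

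**The concern.** The plan names a confounder and a task meant to deal with it, but specifies no analysis in which the task does so. Collecting a measure removes no confounding until a model uses it.

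The weak place is path b. The intervention is randomised but the mediator is not, so anything that drives both connectivity and later self-regulation biases b. The plan's own material makes impulse control a credible candidate. In the resting-state pilot of 25 children (IIC.3e), impulsivity correlated negatively with ventral striatum–ACC connectivity, and both regions are planned seeds. The outcome index (IIIC.4f.2a) has seven measures, two of which are self-control and impulsivity.

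The H1 trigger for covariates would not catch this. It looks for group differences, whereas confounding of path b can be present when the groups are perfectly balanced.

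At stake is the claim that connectivity change carries the PAAS effect, when part of the b coefficient may reflect stable differences in impulse control.

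**Working it through.** **Tracing the task.** No figure in the plan bears on this point, so the first check is textual.

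- IIIC.1: supplementary measure; no rule for its use.
- IIIC.4f.2b.6: a within-task contrast. The gPPI connectivity method that follows is not restricted to WOF, so Go/No-Go connectivity could be compared between groups, but nothing links it to WOF.
- IIIC.5 and IIIC.7c: general permission for supplementary or covariate use; Go/No-Go is not named.
- IIIC.7d covariates: absent.
- IIIC.7d.1 and IIIC.7d.2: absent as outcome, covariate and mediator.
- IIIC.7d.3 (exploratory): not named.

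**Illustrating the bias in path b.** N = 102 comes from IIIC.6 and two-tailed alpha .05 from IIIC.7e. Everything else is assumed, because the documents give no correlation between No-Go performance and connectivity or self-regulation. Let baseline impulse control correlate c with mediator and outcome at both times, with true b = 0.

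Step 1, adjusting for the intervention only (IIIC.7d.2). The spurious correlation is r = c × c, that is .09, .16 and .25 for c = .3, .4 and .5. By Fisher's z, the chance of p < .05 is Φ(atanh(r)·√98 − 1.96) + Φ(−atanh(r)·√98 − 1.96), where 98 = 102 − 3 − 1. For c = .5: atanh(.25) = .2554, times 9.90 gives 2.53, and Φ(0.57) = .715. The three results are .145, .359 and .715. A noncentral F calculation gives .148, .368 and .733.

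Step 2, also adjusting for Phase 1 self-regulation (IIIC.1). With outcome stability s between .5 and .7, the partial correlation is c²(1 − s) / √[(1 − c⁴)(1 − s²)]. For c = .5 and s = .5: .125 / √(.9375 × .75) = .125 / .8385 = .149, a rate of about 32%. For s = .7: .075 / √(.9375 × .51) = .108, about 19%.

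Step 3, also adjusting for Phase 1 connectivity, with assumed stability .4 to .6. The partial correlation comes from inverting the correlation matrix of the four mediator and outcome values.

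| c | Intervention only | + Phase 1 outcome | + Phase 1 connectivity |
|---|---|---|---|
| .3 | 14.5% | 7–8% | 5–6% |
| .4 | 36% | 10–15% | 6–9% |
| .5 | 72% | 19–32% | 9–18% |

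At c = .2 the rate is about 7% even in the first column.

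Step 4, adding the baseline impulse-control measure. In this set-up the partial correlation becomes exactly zero. In practice this holds only as far as the No-Go error rate captures impulse control. The task yields about 98 No-Go trials per scan session (2 × 245 × .20), from which an error rate can be computed.

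These rates are for path b alone. A false mediation finding also needs path a to be significant, so the table shows what happens when PAAS does shift connectivity.

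**The case against.** Four counter-arguments deserve weight.

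*The task is not idle.* A reader might infer that the safeguard does nothing. The documents do not support that: Go/No-Go has a specified contrast, the gPPI analysis is not confined to WOF, and IIIC.5 and IIIC.7c leave room for supplementary or covariate use. The defect is an unspecified use, not the absence of any use. A general permission still does not ensure anything.

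*H1 is not confounded.* A reader might also infer that the H1 group effect is biased. Randomisation protects it from baseline impulse control. H1 does not claim an effect on reward processing that is absent from inhibition, and PAAS targets self-control, so a parallel effect on inhibition would fit the theory. Requiring the WOF effect to exceed the Go/No-Go effect would add an estimand that H1 does not need and for which IIIC.7e gives no power calculation.

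*The Phase 1 adjustment absorbs much of the bias.* This stands. The Phase 1 index contains the self-control and impulsivity scales, and the table shows the reduction. But the adjustment appears in IIIC.1 and not in the H2 model, and it does not remove the bias at the larger assumed correlations.

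*The sentence in section I concerns risky decision-making and never mentions mediation.* This is true. However, connectivity during that decision-making task is a primary outcome and a candidate H2 mediator, so the same worry carries over.

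**Conclusion.** The concern holds as a gap between a stated purpose and the specified analysis. No H1 or H2 model says how Go/No-Go is used, so the plan does not show how it ensures freedom from confounding by impulse control. The consequence is confined to H2 path b.

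The size is uncertain. It ranges from negligible (shared correlations near .2, or .3 with Phase 1 adjustment) to serious (.5 with the intervention as the only adjustment). The range rests on assumed equal correlations, assumed stabilities and true b = 0. The pilot supports a link between impulsivity and resting ventral striatum–ACC connectivity, but IIC.3e gives no coefficient, and the documents report no such link for WOF connectivity.

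**What to change.** In IIIC.7d.2, state that the mediator and outcome models both include Phase 1 connectivity, Phase 1 self-regulation and the baseline, pre-randomisation No-Go commission error rate, regardless of group balance. State also that the week-6 No-Go value is not adjusted for: PAAS targets self-control, so that value may carry part of the intervention effect.

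Optionally, report the same baseline-adjusted group model for Go/No-Go connectivity from the same seeds as a descriptive supplementary analysis, with no decision rule based on a difference between tasks.

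If the sponsor prefers not to add the covariate, section I should be reworded to match the supplementary role given in IIIC.1.

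The data are already planned. In the H2 outcome model the No-Go term takes residual degrees of freedom from 97 to 96 at N = 102. As a guide to the power cost, a one-predictor test at r = .31 has power .903 with or without one extra covariate that explains nothing.
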